## **11 INVESTIGATOR OBLIGATIONS**

### **11.1 Regulatory Documentation**

Before the trial starts, Essential Documents as defined in ICH E6 will be generated and placed in both the Investigator's and Sponsor's files. Additional Essential Documents will be added to both files as new information becomes available and at the completion or termination of the trial as defined in ICH E6.

### **11.2 Protection of Human Subjects**

#### **11.2.1 Declaration of Helsinki**

The Investigator will conduct this study in accordance with the Declaration of Helsinki (1964) including all amendments up to and including the October 2013 revision.

#### **11.2.2 Good Clinical Practice and Regulatory Compliance**

The Investigator will conduct this study in accordance with the principles of GCP (current ICH guidelines) and the requirements of all local regulatory authorities regarding the conduct of clinical trials and the protection of human subjects.

The study will be conducted as described in the approved protocol, with amendments and in accordance with the obligations of clinical Investigators set forth in the Form FDA 1572 and in 21 CFR 50, 54, 56 and 312.

#### **11.2.3 Institutional Review Board**

The Investigator is responsible for the submission of the protocol, ICF, and other written materials (such as advertisements and diaries), along with relevant supporting data (e.g., IB), to the appropriate IRB for review and approval before the study can be initiated. The Investigator is also responsible for submitting amendments to the protocol and ICF to the IRB for review and approval prior to implementation of the change. The Investigator is responsible for providing the Sponsor with a letter documenting the IRB approval prior to initiation of the study or implementation of the changes, respectively.

The Investigator will not have authority to implement any deviation or change to the protocol without prior review and documented approval/favorable opinion from the IRB of an amendment, except where necessary to eliminate an immediate hazard to study subjects. Any significant deviation from the approved protocol will be documented in the source documents and eCRF.

Any deviation or change to the protocol required to eliminate an immediate hazard prior to obtaining IRB approval/favorable opinion, will be submitted as soon as possible to:

- IRB for review and approval/favorable opinion.

- The Sponsor via appropriate designees.
- Regulatory Authorities, if required by local regulations.

Documentation of IRB approval signed by the chairperson or designee of the IRB will be provided to the Sponsor via appropriate designees.

If an Amendment substantially alters the study design or increases the potential risk to the subject: (1) the ICF will be revised and submitted to the IRB for review and approval/favorable opinion; (2) the revised ICF will be used to obtain consent from subjects currently enrolled in the study if they are affected by the Amendment; and (3) the new ICF will be used to obtain consent from any new subjects prior to enrollment.

The Investigator is responsible for informing the IRB of all reportable AEs. IND Safety Reports provided by the Sponsor to the Investigator will be promptly forwarded to the IRB by the Investigator. Updates to the IB provided by the Sponsor to the Investigator will be submitted to the IRB by the Investigator.

The Investigator is also responsible for informing the IRB of the progress of the study and for obtaining annual IRB renewal. The Investigator must inform the IRB when the study is completed or terminated. After completion or termination of the study, the Investigator will submit the final clinical study report to the IRB. The structure and content of the report will meet that described in Structure and Content of Clinical Study Reports E3 (ICH Harmonized Tripartite Guideline, dated November 30, 1995).

#### 11.2.4 Subject Informed Consent

The Investigator must comply with informed consent regulations (21 CFR Part 50) and relevant state regulations (i.e., California Bill of Rights for California patients).

The ICF will clearly describe the nature, scope, and potential risks and benefits of the study, in a language that the subject understands. The ICF will conform to all the requirements for informed consent according to ICH GCP and US FDA guidelines (21 CFR 50) and will include any additional elements required by the Investigator's institution or local regulatory authorities. The ICF will adhere to the ethical principles that have their origin in the Declaration of Helsinki.

Prior to the beginning of the study, the Investigator will obtain the IRB's written approval/favorable opinion of the written ICF. The IRB approved ICF will be given to each prospective participant. The subjects will be given adequate time to discuss the study with the Investigator or site staff and to decide whether or not to participate. Each subject who agrees to participate in the trial and who signs the ICF will be given a copy of the signed, dated, and witnessed document. The original signed ICF will be retained by the Investigator in the study files.

The ICF and any other information provided to subjects will be revised whenever important new information becomes available that is relevant to the subject's consent, and the Investigator will obtain the IRB's written approval/favorable opinion prior to the use of the revised documents. The Investigator, or a person designated by the Investigator, will fully inform the subject of all pertinent aspects of the study and of any new information relevant to the subject's willingness to continue participation in the study. Subjects will read and sign any and all revised ICFs.

### **11.3      Subject Confidentiality**

All information obtained during the conduct of the study with respect to the subjects' state of health will be regarded as confidential. This is detailed in the ICF provided to the subject. An agreement for the use or disclosure of any such information (PHI) will be obtained from the subject in writing (HIPAA authorization) prior to performing any study-related procedures. Disclosure of subject medical information obtained as a result of this study to third parties other than those noted below is prohibited.

Medical information resulting from a subject's participation in this study may be given to the subject's personal physician or to the appropriate medical personnel responsible for the subject's welfare. Data generated as a result of this study are to be available for inspection on request by FDA or other government regulatory agency auditors, the Sponsor (or designee), and the IRB.

The information developed in this clinical study will be used by the Sponsor in the clinical development of the Study treatment and therefore may be disclosed by the Sponsor as required for disclosure as a public company to other clinical investigators, to other pharmaceutical companies, to the FDA, and to other government agencies. All reports and communications relating to subjects in this study will identify each subject only by their initials and subject number.

### **11.4      Electronic Data Capture**

All data required by the study protocol will be recorded in the electronic database. Data from the source documents will be entered into the EDC system by authorized Investigational Site personnel. The data will be updated at the time of each subject visit. Results of tests performed outside the Investigational Site will be entered as soon as available to the Investigational Site. The Principal Investigator must verify that all data entries are accurate and correct by electronically signing the subject's Investigator signature screen.

### **11.5      Source Documentation**

All data entered in the eCRF must be verifiable against source documentation. Source documents may include, but are not limited to, a subject's medical record, hospital charts, clinic charts, the Principal Investigator's study files, as well as the results of diagnostic tests.

### **11.6      Retention of Records**

The Investigator has the responsibility of maintaining a comprehensive and centralized filing system containing all study-related documentation. These files must be available for inspection by the Sponsor or designee, the IRB, and regulatory authorities (i.e., FDA or international regulatory authorities) at any time and should consist of the Essential Documents as defined in ICH E6, which include, but are not limited to, the following elements:

- Subject files, containing the completed eCRFs, supporting source documentation from the medical record, including laboratory data, and the signed ICF;
- Regulatory files, containing the protocol with all amendments and Sponsor and Investigator signature pages, copies of all other regulatory documentation, and all correspondence between the site and the IRB and Sponsor; and

- Drug accountability files, including a complete account of the receipt and disposition of the Study treatment (active and placebo).

The Investigator will retain all study records for at least 2 years after the last approval of a marketing application in an ICH region (i.e., United States, Europe, or Japan), and until there are no pending or contemplated marketing applications in an ICH region. If no application is filed or if the application is not approved for such indication, the Investigator will retain all study records for at least 2 years after the investigation is discontinued and regulatory authorities have been notified. The Sponsor will provide written notification when it is appropriate for the Investigator to discard the study-specific documents referenced above.

The Investigator will notify the Sponsor prior to destroying any study records. Should the Investigator wish to assign the study records to another party or move them to another location, the Sponsor will be notified in writing in advance.

If the Investigator cannot guarantee this archiving requirement at the Investigational Site for any or all of the documents, special arrangements will be made between the Investigator and the Sponsor for storage. If source documents are required for continued care of the subject, appropriate copies for storage off site will be made.

## **11.7 Clinical Study Report**

After completion or termination of the study, a clinical study report will be prepared. The structure and content of the report will meet that described in Structure and Content of Clinical Study Reports E3 (ICH Harmonized Tripartite Guideline, dated November 30, 1995). The Principal Investigator must verify that all information and data in the clinical study report is accurate and correct by signing the clinical study report.

# **12 STUDY ADMINISTRATION**

## **12.1 Study Monitoring**

This study will be monitored by the Sponsor or designee to evaluate the progress of the study, to verify the accuracy and completeness of the eCRFs, to assure that all protocol requirements, applicable laws and/or regulations, and Investigator's obligations are being fulfilled, and to resolve any inconsistencies in the study records.

The Investigator will allow the Study Monitor to periodically review, at mutually convenient times during the study and after the study has been completed, all eCRFs and office, hospital, and laboratory records supporting the participation of each subject in the study.

The Study Monitor will compare the eCRF data against source documentation in order to verify its accuracy and completeness. The Investigator and Investigational Site staff will collaborate with the Study Monitor to resolve any identified data discrepancies in a timely manner.

The Study Monitor will record any protocol deviations identified, including, but not limited to, subjects that were enrolled even though they did not meet all eligibility criteria, subjects who took concomitant medications specifically prohibited by the protocol, subjects who received the wrong study treatment or incorrect dose, and subjects who failed to comply with the protocol-defined dietary restrictions. The Investigator and Investigational Site staff will collaborate with the Study Monitor to identify the reason for each protocol deviation.

The Study Monitor will compare the Investigational Site study treatment accountability record against the study treatment inventory (unused and used) at the site. The Investigator and Investigational Site staff will collaborate with the Study Monitor to resolve any identified discrepancies in a timely manner.

Each issue identified during study monitoring visits will be documented and reported to both the Sponsor and the Investigator.

## **12.2 On-Site Audits**

The FDA, or other regulatory authorities, may request access to all study records for inspection and copying. The Principal Investigator and Investigational Site staff will cooperate with the inspectors and allow access to all source documents supporting the eCRFs and other study-related documents. The Investigator will immediately notify the Sponsor when contacted by any regulatory authority for the purpose of conducting an inspection.

The Sponsor or designee may also request to visit the Investigator's site to conduct an audit of the study. Prior to initiating this audit, the Investigator will be contacted by the Sponsor to arrange a convenient time for this visit. The Principal Investigator and Investigational Site staff will cooperate with the auditors and allow access to all source documents supporting the eCRFs and other study-related documents.

## **12.3 Data Quality Assurance**

All eCRFs must be completed by authorized Investigational Site personnel who have undergone eCRF training. Data will be entered into the eCRF as information becomes available on a visit-by-visit basis. All data recorded on the eCRFs must be supported by source documentation. The Principal Investigator must verify that all data entries in the eCRF are accurate and correct by electronically signing and dating the eCRF.

All eCRF corrections must be made by the Principal Investigator or authorized Investigational Site personnel. The Principal Investigator must authorize changes to the recorded data, and this authorization must be documented in the source documents.

Refer to [Section 9](#) for further details regarding Data Management quality assurance, including query generation and resolution, final data review, and database lock.

## **12.4 Publication Policy**

All information and data obtained in the course of the study are the property of the Sponsor and are considered confidential. To avoid disclosures that could jeopardize proprietary rights, the

institution and/or the Investigator agree to certain restrictions on publications (e.g., abstracts, speeches, posters, manuscripts, and electronic communications), as detailed in the clinical trial agreement.

The publication or presentation of any study results shall comply with all applicable privacy laws, including, but not limited to, HIPAA or equivalent.

This trial will be registered in a publicly accessible database (clinicaltrials.gov) not later than 21 days after enrollment of the first subject. Results of this trial, including negative and inconclusive, as well as positive results, will be made publicly available.

## **12.5 Disclosure and Confidentiality**

By signing the protocol, the Investigator agrees to keep all information provided by the Sponsor and Integrium in strict confidence and to request similar confidentiality from his/her staff and the IRB. Study documents provided by the Sponsor and Integrium (protocols, IBs, eCRFs, and other material) will be stored appropriately to ensure their confidentiality. The information provided by the Sponsor and Integrium to the Investigator may not be disclosed to others without direct written authorization from the Sponsor and Integrium, except to the extent necessary to obtain informed consent from subjects who wish to participate in the study.

## 14 APPENDIX A

### 14.1 Guidelines for TRACER Infusion

#### EGP Protocol

**Tracer:** [6,6-H2]-glucose (from Cambridge Isotope Laboratories

[<https://shop.isotope.com/productdetails.aspx?itemno=DLM-349-PK>])

**Constant tracer infusion rate:**  $0.28 \text{ } \mu\text{mol} \cdot \text{min}^{-1} \cdot \text{kg}^{-1}$  ( $= 51 \text{ } \mu\text{g} \cdot \text{min}^{-1} \cdot \text{kg}^{-1}$ ) via an indwelling catheter in an antecubital vein. Assuming participants have dinner at 18:00pm, the tracer infusion can start at 20:00pm and continue until 12 noon the following day, *i.e.*, for 960 min.

**Example:** In a T2D subject weighing 90 kg, the total amount of tracer would be  $0.28 \times 960 \times 90 = 24,192 \text{ } \mu\text{mol}$  ( $= 4.41 \text{ g}$  per study). Rounding this up, one dissolves 4.5 g of [6,6-H2]-glucose in 500 mL of saline: this is the mother solution (from which a 5 mL aliquot must be saved together with the plasma samples) to be given at a rate of 0.5 mL/min to the 90-kg person for 960 min.

**Blood sampling:** through a cannula in a contralateral antecubital vein, one sample is taken prior to starting the tracer infusion, then blood is drawn every hour till the end.

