## 1 INTRODUCTION

Endogenous insulin – secreted by the  $\beta$ -cells of the endocrine pancreas – flows to the liver in the portal blood before reaching the systemic circulation through the hepatic veins. Following oral administration, the insulin in ORMD-0801 is absorbed through the gastrointestinal mucosa into the mesenteric veins (mostly, the superior mesenteric vein that drains blood from the jejunum and ileum) and reaches the liver *via* the portal vein, thereby mimicking the route of entry of endogenous insulin. The main action of insulin in the liver is to suppress glucose production; for this action, sensitivity is higher, and onset and offset time of this action are faster than for insulin stimulation of glucose uptake by peripheral tissues. First-pass extraction of insulin by the liver is 50-60%; recirculation raises this percentage to ~80%. As a consequence, portal plasma insulin concentrations normally are ~3-fold higher than peripheral insulin levels.

The hypothesis behind ORMD-0801 is that sufficient oral insulin survives gastrointestinal degradation to arrive at the liver where it inhibits glucose production and, through this effect, lowers fasting plasma glucose concentrations. As the majority of this exogenous insulin dose is degraded in the liver, the resulting systemic insulin levels may be only marginally increased, thereby avoiding the risk of hypoglycemia.

The use of glucose tracers is the standard non-invasive approach to measure endogenous glucose production (EGP). A tracer (in this protocol, [6,6-H2]-glucose, a stable isotope of glucose) infused intravenously at a constant rate will equilibrate with endogenous glucose across its distribution space within ~3 hours. From this time onward, the ratio of the tracer infusion rate to the plasma tracer/tracee ratio (as assayed by GCMS) measures EGP. As compared to placebo, oral insulin is expected to reduce EGP over the ensuing 13 hours of continued fasting. In patients with type 2 diabetes, EGP is known to be abnormally elevated and to contribute the hyperglycemia. Oral insulin is therefore addressing a key pathophysiological derangement of type 2 diabetes.

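### The 90-kg tracer example in Appendix A delivers 50 µg/kg/min, 2% below the 51 µg/kg/min it is meant to illustrate, and the plan does not say which rate enters the EGP formula

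*Combined protocol and SAP*

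**What the plan says.** Section 14.1 (Appendix A) gives one constant infusion rate in two units, 0.28 µmol/kg/min and 51 µg/kg/min. The infusion is to "continue until 12 noon the following day, *i.e.*, for 960 min". For a 90-kg subject the appendix derives a requirement of 24,192 µmol, or 4.41 g. It then goes to the bench recipe: "Rounding this up, one dissolves 4.5 g of" the tracer in 500 mL of saline, "to be given at a rate of 0.5 mL/min to the 90-kg person for 960 min". A 5 mL aliquot of this solution must be kept with the plasma samples; what it is for is not stated.

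The Introduction says that once the tracer has equilibrated, EGP is measured by "the ratio of the tracer infusion rate to the plasma tracer/tracee ratio". It does not say whether that rate is the nominal one or the one actually delivered. Sections 6.2.1, 8.3 and 8.4.1 list the EGP parameters and the analysis model but give no rule for computing EGP. The opening of Section 8 defers further detail to the statistical analysis plan, and the text supplied contains no such rule. No preparation rule is given for body weights other than 90 kg.

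**The concern.** Rounding the mass up from 4.41 g to 4.5 g reads as a small safety margin. It is not one, because the pump setting empties only 480 of the 500 mL. The subject therefore receives less than the stated rate, not slightly more.

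The rate is the numerator of the EGP formula, so a relative error in it passes one-for-one into every EGP value and into AUC(0-16), the primary parameter. The only rate the documents name is the nominal one, and an analyst without further instruction could well use it. At stake are the absolute scale of EGP and the size of the estimated treatment difference. There could also be some extra variability, if the error differed between subjects.

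**Working it through.** **Inputs from Section 14.1:** nominal rate 0.28 µmol/kg/min = 51 µg/kg/min; weight 90 kg; duration 960 min; 4.5 g in 500 mL; pump rate 0.5 mL/min. **Assumption, not in the documents:** molar mass 182.17 g/mol. The appendix's own figures imply 51/0.28 = 182.1 and 4.41 g/24,192 µmol = 182.3, so this choice hardly matters, and the comparison in mass units does not need it.

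**1. The appendix's nominal figures reproduce.**
- 0.28 × 182.17 = 51.01 µg/kg/min
- 0.28 × 960 × 90 = 24,192 µmol
- 24,192 × 182.17 / 10⁶ = 4.407 g, stated as 4.41 g

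**2. What the recipe delivers.**
- Concentration: 4,500 mg / 500 mL = 9.0 mg/mL
- Rate: 9.0 × 0.5 = 4.5 mg/min; 4,500 µg/min / 90 kg = 50.0 µg/kg/min
- In molar units: 50.0 / 182.17 = 0.2745 µmol/kg/min
- Total: 0.5 × 960 = 480 mL; 480 × 9.0 mg = 4.32 g

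**3. Size of the gap.**
- 50.0 / 51 − 1 = −2.0%; 4.32 / 4.41 − 1 = −2.0%
- Cause: 480/500 = 0.960 (−4.0%) and 4.5/4.407 = 1.021 (+2.1%); the product is 0.980
- EGP from the nominal rate relative to EGP from the delivered rate: 0.28 / 0.2745 = 1.020, about 2% too high

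**4. Other body weights.** The documents give no rule, so these are scenarios.

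| Assumed rule | Delivered rate relative to nominal |
|---|---|
| Same 9 mg/mL solution, pump rate scaled to weight | −2.0% in every subject |
| 500 mL at 0.5 mL/min, mass rounded up to next 0.1 g, 55–120 kg | −4.0% to −2.0% on whole-kg weights; −4.0% to −0.6% on weights to 0.1 kg (SD about 0.75%) |
| 500 mL at 0.5 mL/min, mass rounded up to next 0.5 g, 55–120 kg | −3.9% to +10.7% on whole-kg weights; −4.0% to +11.9% on weights to 0.1 kg (SD about 3.6%) |

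The SDs take weights evenly spread over the range.

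**5. Effect on the comparison, if the nominal rate is used.**
- Constant error: every EGP value is multiplied by about 1.02. The ANOVA test statistic and p-value do not change; the estimated difference is multiplied by about 1.02.
- Varying error: the endpoint SD is inflated by about √(1 + (SD of error / CV)²). Assume a between-subject CV for EGP of 15% to 30% (not in the documents). An error SD of 0.75% then adds 0.03% to 0.12% to the endpoint SD, and an error SD of 3.6% adds 0.7% to 2.8%.

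**The case against.** The strongest reply is that the 2% may never reach an EGP value. No section says EGP is computed from 0.28, and the saved 5 mL aliquot would let the laboratory measure what was infused. That stands: the error in EGP is conditional, and what is established is a contradiction in the recipe plus silence on which rate is used. The aliquot does not close the gap by itself, since the documents do not say that it is assayed or that the result enters the calculation.

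A second reply is that the gap is a matter of printed precision. The 9 mg/mL solution would have to run at 51 × 90 / 9,000 = 0.51 mL/min to give 51 µg/kg/min, which rounds to the printed 0.5. Some solution must also remain for the aliquot. This may explain the gap. It does not remove it, because a pump set as written delivers 50.

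A reader might go further and infer that the error differs from subject to subject and so adds real noise to the primary endpoint, by up to about 11% at some weights. The documents do not support that. The appendix gives one example, states the pump rate for the 90-kg person only, and is compatible with scaling the pump rate to weight, in which case the error is the same 2% in everyone. The wider ranges come from rounding rules assumed for illustration, and they move with the fineness of the weight grid. Nor do the documents support an inference of bias between arms: allocation is randomized and blinded, and tracer preparation does not depend on it.

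**Conclusion.** The contradiction is established from the appendix's own figures: followed as written, the 90-kg example delivers 50.0 µg/kg/min and 4.32 g, not 51 µg/kg/min and 4.41 g, a shortfall of 2.0%. If EGP were computed from the nominal 0.28, it would be about 2% too high in that example. Whether it would be is not stated.

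The consequence is modest. It falls on the absolute EGP scale and on the estimated difference, each by about 2%; no between-arm bias is expected, and under a constant error the test is unaffected. Added noise is possible only if mass is rounded by weight at a fixed pump rate. Under the assumed CVs it is negligible with 0.1 g rounding and small even with 0.5 g rounding. The point still merits correction, because this is an operational instruction that does not deliver its own stated rate, and that rate is the numerator of the primary endpoint.

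**What to change.** 1. In Section 14.1, reconcile the example's mass, volume and pump rate with the stated constant rate, so that both give the same µg/kg/min. Which figures to change is for the sponsor to decide. Give the preparation rule for other body weights in the same place.
2. In the statistical analysis plan, state that each subject's EGP uses the delivered rate rather than the nominal 0.28: assayed concentration of the saved 5 mL aliquot × recorded pump rate / Day 28 body weight, converted to molar units.

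The cost is one appendix correction and one sentence of analysis text. The aliquot is already required and weight is already measured on Day 28 (Section 3.4.1). The added work is assaying one aliquot per subject and recording the actual pump rate. With the delivered rate in the formula, the 2% question disappears whichever preparation rule the sites follow.
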